Feasibility will be assessed by 1) collecting measures including cardiometabolic risk (e.g. blood pressure and blood draw – lipid profile, inflammation), body composition (DXA), dietary assessments (NHANES diet screening questionnaire and skin carotenoid assessment), and cognitive assessments (NIH toolbox), 2) recruitment throughout the intervention including reasons for refusal to participate and 3) retention rates including attrition (80% compliant) rate of completion of the intervention (i.e. number/percentage of participants who complete all aspects of the intervention including cooking classes and coach directed dietary call support).

Acceptability will be assessed post-intervention using two REDCap online surveys,³ that will capture the overall experience and perception of the MIND+SOUL diet. For the first survey acceptability will be evaluated on the theoretical framework of acceptability and evaluate the following constructs⁴: affective attitude (how an participant feels about the MIND+SOUL intervention), burden (perceived amount of effort required to participate in the MIND+SOUL intervention), ethicality (extent to which the intervention has good fit with the participants value system), perceived effectiveness (extent to which the intervention is perceived as likely to achieve its purpose), and self-efficacy(participants confidence that they can perform the behaviors required to participate in the intervention). The second survey will evaluate satisfaction with the MIND+SOUL diet using a visual analog scale.

Secondary Outcomes

Data from our secondary outcomes will form the basis of estimating power and sample size for a future randomized controlled clinical trial.

Baseline descriptive statistics including demographic, psychosocial, dietary and behavioral characteristics will be measured.

Cardiometabolic risk: Cardiometabolic risk will be measured by 2 items; blood pressure and blood draw. Blood pressure will be measured using the Omron 5 series blood pressure monitor.⁷ Blood draw will be administered to collect measurements of lipid profile, glucose metabolism, inflammation, APOE-

$\epsilon 4$ genotyping, and other AD related fluid cardiometabolic biomarkers. All cardiometabolic risk assessments will be collected at baseline and at the 12-week mark.

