1. *Informed Consent:* The participant will be provided with a copy of the consent form at least one day prior to the consenting session, either via mail, email, or REDCap. A member of the study team will review the consent form, in its entirety, with the patient, typically in person at the baseline visit. In some instances, a participant may request to conduct the consenting session remotely and prior to the baseline visit, to keep the time in clinic to a minimum, or if other obligations (such as work commitments) limit their availability. The study team will answer all questions before obtaining the participant's written or electronic signature (via REDCap) indicating their consent. Once the consent form is also signed by the person obtaining consent, a copy of the fully signed document is returned to the participant. If consent was conducted remotely, a copy of the fully signed consent form may be returned to the participant in person at the baseline visit, or through email via REDcap.
2. *Medical History:* The medical history information that was gathered from the participant during the phone pre-screen to determine eligibility will be reviewed and updated if necessary. The study team will also record participant's current medications.
3. *Final Review of Eligibility:* As all eligibility criteria were assessed during the phone screen, with the exception of Exclusion Criterion (f): *uncontrolled blood pressure, blood pressure will be checked first (using the Omron 5 series blood pressure monitor⁷)*. In addition, the study team will review all other eligibility criteria with the participant to ensure there have been no changes in eligibility status since the phone pre-screen. The PI will confirm the participant meets all eligibility criteria before proceeding with the rest of the baseline measures.
4. *Dietary assessments:* Nutritional health status change will be measured using the NHANES Dietary Screener Questionnaire and the skin carotenoid assessment (Veggie Meter).⁹
5. *Body composition:* Body composition will be measured using dual energy x-ray absorptiometry (DXA)^{5,6}, weight, and waist circumference.
6. *Cardiometabolic risk:* Blood pressure will be measured immediately following informed consent, as described above in #2. Blood draw will be administered to collect measurements of lipid profile, glucose metabolism, inflammation, APOE-ε4 genotyping, and other AD related fluid cardiometabolic biomarkers.

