Counseling: Counseling: Counseling will consist of one-on-one sessions with a health coach who will provide MIND+SOUL diet continued education and on-going support throughout the diet intervention. This support will consist of education and recommendations specific to the participant's needs, preferences, and local context. The health coach will help participant set dietary goals in relation to the MIND+SOUL diet, help participants develop an action plan for certain situations (i.e. holiday parties, vacations), and provide encouragement in regards to the formation of healthy eating habits. Zoom conference calls will occur bi-weekly for 12-weeks. Each Zoom conference (6 total per participant) is anticipated to last 15-20 minutes each time, with exception to the first Zoom conference call which is anticipated to up to 30 minutes.

Financial support: To improve adherence to the MIND+SOUL diet each participant will receive weekly groceries worth up to \$50 per week (total average of \$600) that will be provided to each participant for 12-weeks. Groceries will be limited to foods within the 10 distinct food groups of the MIND+SOUL diet. These foods will be selected from each week from a community supermarket.

C. Sample size, statistical methods, and power calculation

Single arm: Participants will be in a single arm trial using 3 cohorts (cohort 1 – 10 people, cohort 2 – 10 people, cohort 3 – 10 people). Rationale: Use of a single arm trial will allow for assessment of feasibility and acceptability of the MIND+SOUL diet. Additionally, use of 3 cohort will allow for an opportunity to make revisions between each cohort to further enhance feasibility and acceptability of the MIND+SOUL diet.

Individuals deemed eligible will be placed into 1 of 3 cohort.

Sample Size: A total of 30 participants will be enrolled in the pilot study. Cohort 1 will consist of 10 participants, cohort 2 will consist of 10 people, and cohort 3 will consist of 10 people.

D. Subject Criteria:**1. Inclusion Criteria**

- a. Identify as African American or Black
- b. Age 55 and older
- c. English Speaking
- d. 1 or more of the following CVD risk factors (high blood pressure, high cholesterol, controlled type 2 diabetes overweight/obesity with a BMI of 25 or more as calculated from weight and height at baseline visit)
- e. Cognitively Normal with an AD8 <2 (normal cognition)

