- f. Females of child-bearing potential (i.e., pre-menopausal) must have a negative urine pregnancy test at the screening visit and must agree to use of contraception throughout the trial. The approved methods of contraception are abstinence, the consistent use of an approved oral contraceptive (birth control pill or "the pill"), an intrauterine device (IUD), hormonal implants, contraceptive injection, double barrier method (diaphragm with spermicidal gel or condom with contraceptive foam).

2. Exclusion Criteria

- a. No CVD risk factors
- b. AD8 equal to or greater than 2
- c. Diagnosed with type 1 diabetes
- d. Uncontrolled diabetes type 1 or type 2
- e. Existing diet plan that subject is unable to pause during trial
- f. No internet connection
- g. Uncontrolled hypertension, by history, or as indicated by sitting systolic blood pressure >165 mmHg or diastolic blood pressure >95 mmHg at the baseline visit. If an initial blood pressure reading is higher than this, an additional attempt (at this visit or on another day) could be used before excluding a patient for uncontrolled hypertension
- h. Neurological diseases that impact cognition
- i. Other medical conditions likely to be negatively impacted by a diet change or that could confound the study data (i.e. Celiac Disease, Ulcerative Colitis)
- j. Unable or unwilling to provide written consent
- k. PI determination that study is unsafe or unsuitable for the participant
- l. Active depression as determined by a score of 5 or above on the PHQ9 and deemed to be clinically significant by the medical monitor

3. Withdraw/Termination criteria:

- a. There is no withdraw or termination criteria
- b. Participants are allowed to participate in other observational studies during their enrollment period, but not interventional trials

Total enrollment is anticipated to last between 3-4 months total, with 1-1.5 months of recruitment per cohort.

E. Specific methods and techniques used throughout the study

This study will require two study visits. Outcome data will be collected at baseline and at the 12 week mark (+/- 2 weeks). The total time commitment for visit 1 is 2.5 hours and visit 2 is 2.5 hours.

Visit 1 – Baseline Evaluation

Estimated duration: 2.5 hours

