Body Composition (30 minutes): At baseline and 12 weeks (\pm 2 weeks), dual energy x-ray absorptiometry (GE Lunar iDXA) will be used to determine fat-free mass, fat mass, and percent body fat. DXA uses very low X-ray doses (0.02mREM) to detect changes in body composition on the order of 1.6-3.8%. Body weight, height and waist circumference will be recorded at baseline and at the 12 week mark (\pm 2 weeks). Weight will be obtained using a digital scale (\pm 0.1 kg; Befour Inc model #PS6600, Saukville, WI) and height will be measured using a stadiometer (Model PE-WM-60-84, Perspective Enterprises, Portage, MI). Body mass index (kg/m²) will be calculated. Waist circumference will be obtained using a calibrated tape.²¹

Dietary Screener Questionnaire (30 minutes): Nutritional health status change will be measured using the NHANES Dietary Screener Questionnaire administered by study personnel.

Skin Carotenoid Content (10 minutes): is a validated, biomarker of fruit and vegetable intake.²⁴⁻²⁶ The "Veggie meter" (Longevity Link Corporation) uses Resonance Raman spectroscopy to non-invasively measure skin carotenoid content. Three measurements will be taken on the fingertip and averaged (total time ~1 minute) by study personnel.

Cognition (30 minutes): Participants will complete a cognitive measurement session at the KU ADRC at the baseline and at the 12-week mark. The NIH Toolbox to assess the following domains: memory, language, reading, vocabulary, processing speed, and executive function.² Specifically the following tests will be administered: NIH-TB List Sorting Working Memory Test, NIH-TB Picture Vocabulary Test,

NIH-TB Oral Reading Recognition Test, and the NIH-TB Pattern Comparison Processing Speed Test, and NIH-TB Flanker Inhibitory Control and Attention. Test will be administered by a psychometrician.

Visit 2 – 12-week Evaluation

Estimated duration: 2.5 hours

At 12 weeks (\pm 2 weeks), participants will return to complete blood draw, blood pressure, DXA scan for body composition, height, weight, waist circumference, dietary screener questionnaire, skin carotenoid assessment, cognitive testing, a check for adverse events, and survey completion (acceptability surveys).

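### As the visit summary is written, the baseline blood pressure endpoint is the eligibility reading, which an upper-only limit selects low; the methods section conflicts with this, and the expected false rise is small

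*Combined protocol and SAP*

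**What the plan says.** Blood pressure is one of two cardiometabolic measures listed under Secondary Outcomes (I.A), taken at baseline and week 12. The same section says the secondary outcomes will be used to plan the power and size of a later randomized trial.

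- **Eligibility check (II.B, baseline item 3).** Blood pressure is the criterion left open after the phone screen: "uncontrolled blood pressure, blood pressure will be checked first (using the Omron 5 series blood pressure monitor". Then "The PI will confirm the participant meets all eligibility criteria before proceeding with the rest of the baseline measures".
- **Endpoint (II.B, baseline item 6).** "Blood pressure will be measured immediately following informed consent, as described above in #2". Item 2 is Medical History; the blood pressure check is item 3.
- **Limit (II.D.2, exclusion (g), repeated in III.B).** A person can be excluded on a history of uncontrolled hypertension, and also on a high measurement: "as indicated by sitting systolic blood pressure >165 mmHg or diastolic blood pressure >95 mmHg at the baseline visit". The limit works in one direction, since no lower bound is set. Before exclusion on a measurement, the rule permits one more try: "If an initial blood pressure reading is higher than this, an additional attempt (at this visit or on another day) could be used". High blood pressure is only one of several qualifying conditions: "1 or more of the following CVD risk factors (high blood pressure, high cholesterol".
- **Device.** Secondary Outcomes says "Blood pressure will be measured using the Omron 5 series blood pressure monitor", the device named for the eligibility check. II.E, Visit 1, instead gives a 10-minute measurement on a DinaMap ProCare 100 under the NHANES protocol.
- **Number of baseline readings.** II.B lists no second baseline measurement, and the schedule has a single blood pressure row. No section says which value is the baseline when there are two attempts.

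**The concern.** A reading that must fall at or below a limit to admit the participant is not a neutral baseline. Among people near 165/95, those whose error on the day was low are admitted and those whose error was high are retested or excluded. The week 12 reading passes no such screen, so its error averages zero. The difference between the two then contains a rise unrelated to diet, which would partly hide a real fall. With a single arm, nothing in the data separates this from a diet effect.

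The missing rule on repeats is a second, smaller problem. For a retested participant, recording the passing value or the first value can give apparent changes of opposite sign, and the choice is open after the data are seen.

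**Working it through.** **The plan's own figures.** The plan gives no blood pressure distribution and no bias figure. Its one statistical figure (V.A, 80% power, 10 samples at each of 3 time points, magnitude 1.3) comes out at 81.8% for means 0, 0, 1.3 with alpha 0.05 assumed. It has no bearing on this point.

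**Inputs from the plan.** Limits 165 and 95 mmHg; one further attempt, only after a high first reading; no limit at week 12; 30 participants, one arm. Everything else below is assumed.

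**Step 1: hand check of the limit alone.** Write the reading as X = T + e, where T is the person's stable level and e the error on the day. For an upper limit c and z = (c − mean)/SD of X,

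E[e | X ≤ c] = −(σe²/σX) × φ(z)/Φ(z).

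Assume mean 135, SD of the recorded reading 18, within-person SD 10. Then z = (165 − 135)/18 = 1.67, φ = 0.0995, Φ = 0.952, and the expected baseline error is −(100/18) × 0.0995/0.952 = −0.58 mmHg. The expected week 12 error is 0, so the expected change is +0.58 mmHg. This uses the systolic limit only; the simulation in step 2 adds the correlated diastolic limit and gives +0.85.

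**Step 2: simulation with both limits and no diet effect.** Mean systolic change in mmHg. Assumed diastolic mean 78 to 82.5, SD 10, systolic-diastolic correlation 0.6. A same-visit repeat has error correlation 0.7 with the first reading; another-day repeats are independent.

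| Systolic mean / SD / within-person SD | No repeat | Passing repeat recorded, another day | Passing repeat recorded, same visit | First reading recorded, another day |
|---|---|---|---|---|
| 135 / 18 / 10 | 0.85 | 1.02 | 0.77 | 0.22 |
| 140 / 20 / 10 | 1.29 | 1.59 | 1.25 | 0.39 |
| 145 / 20 / 10 | 1.72 | 2.11 | 1.69 | 0.57 |
| 145 / 20 / 12 | 2.49 | 2.94 | 2.32 | 0.73 |

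The limit alone gives most of the shift. The repeat adds to it or reduces it slightly if the passing value is recorded, and reduces it more if the first value is recorded.

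**Step 3: the range quoted.** Assume true systolic mean 130 to 145, between-person SD 14 to 16, within-person SD 8 to 10; true diastolic mean 80 to 84, SDs 8 to 9 and 5 to 6. With the passing value recorded, the systolic shift is +0.5 to +2.2 for another-day repeats and +0.35 to +1.8 for same-visit repeats, hence about 0.3 to 2.2 overall. With no repeat it is +0.4 to +1.8. If systolic and diastolic errors are unrelated, the another-day figures fall to 0.16 to 1.47.

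**Step 4: against sampling error.** The SD of individual change is 11 to 17 mmHg across the step 2 grid. SE = SD/√30, so 11/5.48 = 2.0 to 17/5.48 = 3.1 mmHg. In the largest case, 2.94/(16.3/5.48) = 0.99 SE. In the 135/18/10 case, 1.02/(13.9/5.48) = 0.40 SE, so the chance that the observed mean change is above zero is about 66%, against 50% without selection.

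**Step 5: retested participants.** With another-day repeats, 4 to 11% of those enrolled enter on a retest: 0.04 × 30 = 1.2 to 0.11 × 30 = 3.3 people. Their mean spurious systolic change is +2 to +6 if the passing value is recorded and −5 to −11 if the first is. With a same-visit repeat the passing-value figure is about −1 to +1.

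**Step 6: a separate baseline reading.** If its error is independent of the eligibility reading, the expected shift is 0. With same-visit error correlation 0.7, the simple no-repeat case leaves 0.7 of the shift; with the repeat allowed, about half remained (0.13 to 0.89 mmHg).

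**The case against.** The strongest reply is that the plan may already separate the readings. II.E describes a timed measurement on another device under a named protocol, and II.B says in its opening text that eligibility is confirmed before the assessments are done. That stands: a reader of II.B item 6 might infer that the endpoint and the eligibility reading are definitely the same, and the documents taken together do not establish it. But they do not establish the opposite either, because item 6 and the device in Secondary Outcomes point to the eligibility check.

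Three other stronger readings also fail.

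- A reader might infer that a high reading can be repeated without end. The rule allows one additional attempt.
- A reader might infer that blood pressure would visibly rise by week 12. The expected shift is at most about one standard error, and a reading taken on arrival may run high for unrelated reasons, which would act the other way. The documents give no figure for that.
- A reader might infer different conditions at the two visits from the Visit 2 list, "participants will return to complete blood draw, blood pressure, DXA scan for body composition". The Visit 1 list in II.E has the same order, and II.B calls the week 12 evaluation identical to baseline. These lists are inventories and show no difference in procedure.

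The size may also be somewhat overstated. Exclusion by history removes some people on their stable level; excluding true levels above 165/95 in a check cut the systolic shift by about 15 to 25%.

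**Conclusion.** The point holds in a limited form. The sections conflict on whether the baseline endpoint is the eligibility reading. If II.B is followed, the expected change with no diet effect is a systolic rise of about 0.3 to 2.2 mmHg with the passing value recorded, under the step 3 assumptions. Wider assumptions reach 2.9, unrelated systolic and diastolic errors lower the range, and recording the first value gives 0.05 to 1.6 across the wider grid. The direction follows from the one-sided limit; the size rests entirely on assumed distributions. The unstated recording rule affects roughly one to three people but can change the sign of their apparent change.

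Priority is low to moderate. Blood pressure is a secondary outcome of a 30-person feasibility pilot, no test or threshold for it is specified, and the primary aims are untouched. It merits correction because the estimate is meant to inform the next trial.

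**What to change.** 1. Reconcile Secondary Outcomes, II.B and II.E on the device and protocol for the blood pressure endpoint.
2. Leave the eligibility check, its limits and its repeat rule unchanged, but do not use its reading as the endpoint.
3. After eligibility is confirmed, take the blood pressure set described in II.E in every participant, whatever the eligibility reading was, and define that as the baseline. Use the same device, number of readings and place in the visit at week 12.
4. Record all eligibility attempts, and state that none of them enters the analysis of change.
5. Correct the cross-references: item 6 should point to the new set rather than to item 2, and II.B and III.B should cite the blood pressure criterion as (g), not (f).
6. State in the report that some selection shift can remain, because a separate reading at the same visit shares part of its error with the eligibility reading. The shift is removed fully only if those errors are independent.

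The cost is protocol wording and a few minutes at baseline; II.E already allots 10 minutes to this measurement.

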The participant may be given a copy of their results related to their blood pressure, blood draw results, and body composition if they request it. The data will not be reviewed by the research team or a physician for the presence of clinically relevant abnormalities.

F. Risk/benefit assessment:

1. **Physical risk**
 - a. Blood draw: Participants May feel soreness, swelling, and bruising at the puncture site during the blood draw. This should go away within a day. Good clinical practice guidelines will be followed for biospecimen sampling.
 - b. DXA: There is always a slight chance of cancer from excessive exposure to radiation. However, given the small amount of radiation used in medical imaging, the benefit of an accurate diagnosis far outweighs the associated risk.
 - c. Food consumption: There is a chance that participants may experience gastrointestinal symptoms when consuming foods on the MIND+SOUL diet including but not limited to: nausea, vomiting, diarrhea, acid reflux, heartburn, indigestion, bloating/excess gas, hiccups, halitosis, cramping, abdominal pain, irritable bowel syndrome, constipation, change in bowel movements, and hemorrhoids, gallstones.
2. **Psychological risk.** There is minimal risk for psychological distress due to the nature of the research topic.
3. **Social risk.** There is minimal risk due to the nature of the research topic.
4. **Economic risk.** There is minimal risk due to the nature of the research topic. Participants

will receive up to \$50 worth of groceries each week (\$600 total) for 12 weeks during the study to offset the cost of healthy foods. Focus group participants will receive a \$25 Visa gift card for their participation.

5. Potential benefit of participating in the study

- a. Individuals participating in this study may feel empowered and valued as part of Alzheimer's prevention in the African American community
- b. To the field of Alzheimer's prevention, community participation of this study will help guide future research in the development of culturally appropriate dietary intervention strategies aimed to reduce the risk of cognitive decline specifically for African Americans

G. Location where study will be performed:

Laboratory tests, educational sessions, and skill-building health education/cooking classes, will take place at the KU ADRC. Counseling sessions will take place via Zoom.

H. Collaboration (with another institution, if applicable):

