A. Recruitment: The PI and the Outreach and Recruitment Core at the KU ADRC will contact potential participants through the Clinical Cohort registry via recruitment letter, email, and phone. Secondly, [name] and support personnel will recruit through the delivery of Aging With Grace educational curriculum to faith-based and AA serving organizations and will distribute flyers during each presentation. Lastly, [name] community partners (Bright Business Solutions, BHCC, and Heal Black Men) and consultants will each help recruit AAs through their personal connections and resources. BHCC, Bright Business Solutions, Health Black Men, and consultants will be provided with flyers about the study to provide to their personal connections. Community members who are interested in participating in the study will reach out to the PI or support personnel via email or phone.

B. Screening Interview/questionnaire: The PI or support personnel will provide details regarding the nature of the study, and will conduct an interview to screen for eligibility for the study, following verbal consent from the participant to proceed with the screening questions. This interview will include a review of medical conditions, the completion of the AD8 measure to screen for cognitive impairment, the completion of the PHQ9 measure to screen for active depression, and a review of all eligibility criteria that can be completed prior to baseline to determine eligibility. One eligibility criterion that cannot be completed prior to baseline is Exclusion (f): Uncontrolled hypertension, by history, or as indicated by sittingsystolic blood pressure >165 mmHg or diastolic blood pressure >95 mmHg at the baseline visit. If an initial blood pressure reading is higher than this, an additional attempt (at this visit or on another day) could be used before excluding a patient for uncontrolled hypertension. Individuals deemed eligible via the phone screen will be placed into 1 of 3 cohorts, provided the participant does not meet exclusion criterion (f) at the baseline visit.

C. Alternatives to Participation: none

D. Costs to Subjects: There is no cost to subjects for participation in this study.

E. How new information will be conveyed to the study subject and how it will be documented: No information regarding cardiometabolic health, nutritional status, or cognition will be conveyed to the participant.

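### Testing Results permits release of blood results, which include the APOE-ε4 genotype; III.E bars it, and the risk section considers no such disclosure.

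*Combined protocol and SAP*

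**What the plan says.** Secondary Outcomes (I.A) defines the domain by its two sources: "Cardiometabolic risk will be measured by 2 items; blood pressure and blood draw". There and in the baseline visit list (II.B, item 6, Cardiometabolic risk), the blood draw supplies lipids, glucose measures and inflammatory markers, together with "APOE-ε4 genotyping, and other AD related fluid cardiometabolic biomarkers".

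Three other places bear on what a participant may learn and at what risk:

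- **Testing Results (end of II.E)** on release: "The participant may be given a copy of their results related to their blood pressure, blood draw results, and body composition if they request it". On review: "The data will not be reviewed by the research team or a physician for the presence of clinically relevant abnormalities".
- **Risk/benefit assessment (II.F)** on the blood draw: "Participants May feel soreness, swelling, and bruising at the puncture site during the blood draw". On psychological risk: "There is minimal risk for psychological distress due to the nature of the research topic".
- **III.E (how new information is conveyed)**: "No information regarding cardiometabolic health, nutritional status, or cognition will be conveyed to the participant".

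V.C promises participants a letter on the study's general findings. It does not deal with individual results.

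**The concern.** Staff who receive a request for blood results would find two rules. The sentence in Testing Results allows the copy. The sentence in III.E bars cardiometabolic information. Neither mentions genotype or AD-related biomarkers, although both are among the blood measures.

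The conflict matters more for APOE-ε4 than for a lipid value. Eligibility requires normal cognition (AD8 below 2), and recruitment runs partly through a dementia-prevention curriculum. A genetic risk result for Alzheimer's disease cannot be taken back once given. The stated risks of the blood draw are limited to the puncture site, and the psychological risk statement is a general one tied to the research topic. If Testing Results were followed as written, a participant could receive a result whose disclosure the protocol's own risk assessment has not weighed.

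The safety procedures would not necessarily detect a reaction. The schedule of assessments has one adverse event check, at Week 12, and section K ends adverse event collection at the final study visit. The protocol does not say when genotyping is done, so a disclosure could fall after that.

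**Working it through.** No arithmetic applies: the point rests on no sample size, error rate or effect. The check is to set the sections side by side.

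**Step 1. Is the genotype a blood draw result?** Yes, by the protocol's own lists. Secondary Outcomes and the baseline visit list both name it among the measures from the blood draw.

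**Step 2. Is it a cardiometabolic measure?** Yes, by the protocol's own headings. It is listed under Cardiometabolic risk, and the blood draw is one of the two items that define that domain.

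**Step 3. Apply each rule to the genotype.**

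| Section | Wording that reaches the genotype | Outcome if followed alone |
|---|---|---|
| Testing Results (II.E) | Blood draw results, no analyte excluded | A copy may be given on request |
| III.E | Cardiometabolic health, no exception for requests | Nothing is conveyed |

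The two outcomes are incompatible. Blood pressure is caught in the same way, since it is the other cardiometabolic item. Body composition has its own heading and is not named in III.E, so the conflict there is less direct.

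**Step 4. Does II.F cover the disclosure?** No. It does not mention learning a genotype or a biomarker result.

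**Step 5. Does another section settle it?** No. The blood draw paragraph in II.E describes volume, plasma processing and storage, not return of results. IV.B and IV.C (specimen collection, tissue banking) are marked not applicable. V.C covers general findings only.

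**Step 6. What follows from each way of resolving the conflict?**

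- III.E prevails: no blood result is released, the genotype question disappears, and II.F needs no addition on this account.
- Testing Results prevails unchanged: the genotype stays inside the release, and II.F does not cover it.
- Testing Results prevails with a list of named analytes: the matter is settled either way, provided II.F matches the list.

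Only the second leaves the risk uncovered. The documents do not say which is intended.

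**The case against.** The strongest objection is that the documents as a whole do not release the genotype. III.E, read with the protocol's headings, bars it. Testing Results grants permission on request, not an entitlement, and no section says APOE-ε4 will be reported to anyone. This stands. A reader of Testing Results alone might infer that participants can simply obtain their genotype; III.E prevents that conclusion. It also means the problem is not independent of the conflict between the sections: if III.E governs, it goes away.

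A second objection is that the sections can be harmonised. III.E might mean that the team will not volunteer results, while Testing Results deals with requests. III.E contains no such qualification. Even on that reading the genotype remains within the on-request copy, so the gap in II.F remains.

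Three stronger inferences should not be drawn:

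- **Bias in the outcomes.** A reader might infer that learning the genotype would alter diet effort, the perceived-effectiveness rating or cognitive scores. That requires a result to be available and released before Week 12. The protocol says plasma is stored for analysis and gives no date for genotyping, and it contains nothing on how participants would respond.
- **A count of carriers who would be told.** The documents give no carrier frequency, no request rate and no rate at which requests would be granted.
- **No one looks at the data.** The protocol excludes only review for clinically relevant abnormalities.

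The consent pages are not in the file. Whether participants are told about genetic results there cannot be judged, and nothing here assumes that they are not.

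**Conclusion.** The concern holds as a contradiction with a participant-safety consequence. Testing Results permits, and III.E bars, release of blood results that include the APOE-ε4 genotype and AD-related biomarkers, and II.F does not consider that disclosure. It should be corrected.

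The size is one of scope: both rules apply to all 30 planned participants, and no expected number of disclosures can be derived.

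The finding rests on two readings: that blood draw results means every measure the protocol assigns to the blood draw, and that cardiometabolic health in III.E has the scope of the protocol's own Cardiometabolic risk heading. Both are natural readings, but they are inferences from unrestricted wording. If the sponsor meant a narrower set in either place, the text needs to say so. The finding does not show that the sponsor plans to disclose the genotype, or that any study outcome would be biased.

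**What to change.** 1. Reconcile Testing Results (II.E) and III.E so that they state one rule on individual results, including blood pressure.
2. In Testing Results, replace the general reference to blood results with a list of the analytes that may be returned.
3. In both sections, state whether the APOE-ε4 genotype and the AD-related biomarkers are excluded from the on-request copy.

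Excluding them is the simplest resolution. It agrees with III.E as written and needs no change to II.F. An exclusion alone would not complete step 1, because Testing Results would still allow blood pressure and other blood results that III.E bars.

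If the sponsor instead intends to return the genotype or biomarkers, II.F must address the risk of learning them.

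The cost is a few sentences in two sections and a check that the consent form agrees; return of these results would also need new risk text. The small downside of exclusion is that participants who want their genotype will not get it from this study. No assessment, sample size or analysis changes.
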